11.1.1.1 Adverse Event Severity

The Investigator must determine and record the severity of all serious and non-serious AEs. The Common Terminology Criteria for Adverse Events (CTCAE), Version 4.03, (Cancer Therapy Evaluation Program website; available at: http://ctep.cancer.gov/protocolDevelopment/electronic_applications/ctc.htm ; accessed 01 December 2015) should be used for grading the severity of AEs. AEs of CTCAE Grades 4 and 5 should be documented as "life-threatening."

The severity of an AE that does not appear in the CTCAE scale should be determined according to the definitions below. Clinically significant laboratory tests should be recorded as AEs in the patient's source documents and e-CRF.

Severity will be assessed according to the following criteria:

Classification	Definition
Mild (Grade 1)	Mild level of discomfort and does not interfere with regular activities
Moderate (Grade 2)	Moderate level of discomfort and significantly interferes with regular activities

Severe (Grade 3)	Significant level of discomfort and prevents regular activities
Life-threatening (Grade 4)	Any adverse drug experience that places the patient, in the view of the investigator, at immediate risk of death

11.1.1.2 Adverse Event Causality

Causality will be assessed according to the following criteria:

Classification	Definition
Definitely Related	Reasonable temporal relationship to study drug administration Follows a known response pattern (i.e., drug is known to cause this AE) There is no alternative etiology
Probably Related	Reasonable temporal relationship Follows a suspected response pattern (i.e., based on similar drugs) Little or no evidence for a more likely alternative etiology
Possibly Related	Reasonable temporal relationship Some evidence for a more likely alternative etiology
Not Related	Does not have a temporal relationship. Or, Definitely due to alternative etiology

ICH guidelines (March, 1995) clarify “reasonable causal relationship” to mean “that there are facts [evidence] or arguments to suggest a causal relationship.”

The causality assessment must be made by the Investigator based on information available at the time that the AE/SAE worksheet is completed. The initial causality assessment may be revised as new information becomes available.

11.1.1.3 Study Drug Action Taken

The investigator will classify the study drug action taken with regard to the AE. The action taken should be classified according to the categories shown below:

Classification	Definition
Dose Not Changed	Study drug dose not changed in response to an AE;
Dose Interrupted	Study drug administration interrupted in response to an AE;

Drug Withdrawn	Study drug administration permanently discontinued in response to an AE;
Not Applicable	Action taken regarding study drug administration does not apply. "Not applicable" should be used in circumstances such as when the investigational treatment had been completed before the AE began and no opportunity to decide whether to continue, interrupt, or withdraw treatment is possible.

11.1.1.4 Adverse Event Outcome

An AE should be followed until the investigator has determined and provided the final outcome. The outcome should be classified according to the categories shown below:

Classification	Definition
Recovered/Resolved	Resolution of an AE with no residual signs or symptoms;
Recovered/Resolved with Sequelae	Resolution of an AE with residual signs or symptoms;
Not Recovered/Resolved (Continuing)	Either incomplete improvement or no improvement of an AE, such that it remains ongoing;
Fatal	Outcome of an AE is death. "Fatal" should be used when death is at least possibly related to the AE;
Unknown	Outcome of an AE is not known (e.g., a patient lost to follow-up).

11.1.1.5 Treatment Administered

The Investigator will ensure adequate medical care is provided to patients for any AEs, including clinically significant laboratory values related to study drug. In addition, the Investigator will describe whether any treatment was administered for the AE. "Yes" is used if any treatment was administered in response to an AE and may include treatments such as other medications, hospitalization, surgery, or physical therapy. "No" indicates the absence of any kind of treatment for an AE.

11.1.2 Clinically Significant Assessments

Study assessments including laboratory tests, ECGs, ophthalmological examinations and vital signs should be assessed and those deemed a clinically significant worsening from baseline documented as an AE. When possible, a clinical diagnosis for the study assessment should be provided rather than the abnormal test result alone (e.g. urinary tract infection, anemia). In the absence of a diagnosis, the abnormal study assessment itself should be listed as the AE (e.g. bacteria in urine or decreased hemoglobin).

An abnormal study assessment is considered clinically significant if the patient has one or more of the following:

- Concomitant signs or symptoms related to the abnormal study assessment;
- Further diagnostic testing or medical/surgical intervention;
- A change in the dose of study drug or discontinuation from study drug treatment.

Repeat testing to determine whether the result is abnormal, in the absence of any of the above criteria, does not necessarily meet clinically significant criteria. The determination of whether the study assessment results are clinically significant must be made by the Investigator. A laboratory abnormality judged to be Grade 4, in itself, may not constitute an SAE unless the clinical status of the patient indicates a life-threatening AE.

11.1.3 Serious Adverse Events

SAEs are generally any AEs that result in one or more of the following:

- Fatal (death, regardless of cause, that occurs during participation in the study or occurs after participation in the study but within 30 days post-study, and is suspected of being a delayed toxicity due to administration of the study drug);
- Is immediately life threatening (i.e., presents an immediate risk of death at the time of the AE, not an AE that hypothetically might have caused death if it were more severe);
- Requires or prolongs inpatient hospitalization*;
- Causes persistent or significant disability/incapacity;
- Is a congenital anomaly/birth defect;
- Other important medical events that may not be immediately life threatening or result in death or hospitalization but, based upon appropriate medical judgment, are thought to jeopardize the patient and/or require medical or surgical intervention to prevent one of the outcomes defining an SAE.

*An inpatient hospitalization is defined as an admission for any length of time. A hospitalization for administration of study drug, for routine or planned clinical procedures, or for “social” reasons (not the result of any adverse change in the patient’s condition) should not be considered an AE and should not be reported as a SAE. If the patient experiences any adverse change in condition during hospitalization, the condition must be reported as an AE or SAE according to the above definitions.

For the APPLAUD study, the following AEs may not require expedited reporting based upon the judgment of the Investigator:

- AEs that occur due to Standard-of-Care CF therapies and are consistent with the package labels for such products;
- AEs due to Pulmonary Exacerbation and unrelated to the study drug.

The investigator should consult with the medical monitor if there is any doubt regarding classification of an SAE.

Definition of Life-Threatening Adverse Experience:

An adverse experience is life threatening if the patient was at immediate risk of death from the event as it occurred (i.e., it does not include a reaction that, had it occurred in a more serious form, might have caused death). For example, drug-induced hepatitis that resolved without evidence of hepatic failure would not be considered life threatening, even though drug-induced hepatitis can be fatal.

Definition of Disabling/Incapacitating Experience:

An adverse experience is incapacitating or disabling if the experience results in a substantial and/or permanent disruption of the patient's ability to carry out normal life functions.

Any SAE that occurs during this study, including death from any cause other than disease progression, must be reported to the designated contact for SAE reporting within 24 hours via the e-CRF (preferred), telephone, fax, or email, whether or not related to the study agents. If initially reported via telephone or email, this must be followed up by a e-CRF/written report and submitted within 24 hours of the occurrence of the SAE. Follow-up information after the initial report, including the causality assessment and a narrative, should be sent via e-mail using the paper SAE report form.

Medical Monitor:

[name], Pharmacovigilance Lead
JSS Medical Research

[REDACTED]
[contact]

Additional Medical Contacts may be provided separately for the Australian and European components of the study; they will work in collaboration with [name] of JSS.

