7.2.3 Study / Treatment Arm Stopping Rule Guideline

The following should serve as a guide for the DSMB to recommend stopping the enrolment and/or further drug administration in a given treatment arm. An agreement will be reached with the DSMB on the guideline prior to the study. Other considerations may be used to arrive at such decisions, which must involve Laurent Pharmaceuticals Executive Management.

- Occurrence of any case of death that may be attributed to fenretinide (in such a case, the blind will have to be broken and allocated treatment identified);
- Occurrence of an increased number, relative to placebo, of unexpected SAEs that could be attributable to the drug (at least *probable* causality relationship) that raise Investigators/DSMB concerns about patients' safety;
- Increased frequency and/or severity of drug-related adverse events, relative to placebo, that in the judgment of the Investigators/DSMB, will result in the advice to discontinue fenretinide treatment.

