11.1.3.1 Serious Adverse Event Reporting

It is imperative that the safety desk be informed within 24 hours of an SAE so that reporting to the health authority can be met within the required time frame.

Because of the need to report to health authorities all serious adverse reactions in a timely manner, it is vitally important that an Investigator report immediately any adverse experiences which would be considered serious, even if the Investigator does not consider the adverse experience to be clinically significant or drug related. Should the Investigator become aware of an SAE (regardless of relationship to study drug) that occurs within 4 weeks after the last dose of the study drug, the SAE must be reported in accordance with the procedures specified in this protocol.

All SAEs that are not resolved by the end of the study, or that were not resolved upon discontinuation of the patient's participation in the study, are to be followed until the AE resolves, the AE stabilizes, the AE returns to baseline values (if a baseline value is available), or it is shown that the AE is not attributable to the study drug or study conduct. If a patient or a female partner of a patient becomes pregnant during the study, the patient will be removed from the study without receiving further study medication. Follow-up regarding the outcome of the pregnancy and any postnatal sequelae in the infant is required. Pregnancies are considered immediately reportable AEs (within 1 working day) and are to be documented in the e-CRF.

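### The 24-hour SAE reporting sentence leaves out deaths from disease progression, against the SAE definition and the other reporting rules, so a site could report such a death late

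*Protocol*

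**What the plan says.** Four parts of the protocol govern how a death is reported.

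- **Section 11.1.3, definition.** A serious adverse event includes "death, regardless of cause, that occurs during participation in the study".
- **Section 11.1.3, reporting sentence.** "Any SAE that occurs during this study, including death from any cause other than disease progression, must be reported to the designated contact" within 24 hours, "whether or not related to the study agents". The words at issue are "including death from any cause other than disease progression".
- **Section 11.1.3.1.** "It is imperative that the safety desk be informed within 24 hours of an SAE". Investigators must also "report immediately any adverse experiences which would be considered serious", even when they think the event is neither clinically significant nor drug related.
- **Section 11.1.1.** A serious event within 4 weeks of the last dose goes to the sponsor immediately.

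Two other sections rely on these reports. The first item in the stopping guideline (7.2.3) is "Occurrence of any case of death that may be attributed to fenretinide", in which case the blind is broken. Section 7.3.2 has serious events referred to the DSMB chair as they come in, subject to the DSMB charter, and the chair may ask for unblinding.

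**The concern.** The reporting sentence in 11.1.3 is the one that names the recipient, the clock and the means of reporting, so it is the sentence that site staff are likely to follow. On its natural reading it takes deaths from disease progression out of the 24-hour rule. That makes prompt reporting depend on a cause judged by a blinded investigator at the time of death. The stopping guideline works the other way round: it asks the DSMB to decide, with treatment known, whether a death may be attributable to the drug. If the site's judgement acts as the filter, that assessment may start late.

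The protocol gives its own reasons to want respiratory deaths seen early. Section 5.4 says that earlier attempts to control inflammation in the CF lung led to frequent exacerbations and serious adverse events. Section 7.2.2 asks the DSMB to pay particular attention to the incidence of pulmonary exacerbations.

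**Working it through.** No arithmetic applies; the check is a comparison of texts.

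**Step 1. Does each rule cover a death that the site attributes to disease progression?**

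| Text | Covered? | Timing |
|---|---|---|
| 11.1.3, definition | Yes, during participation, whatever the cause | None; it defines seriousness |
| 11.1.3, reporting sentence | Excluded on the natural reading | 24 hours |
| 11.1.3.1 | Yes, no exception by cause | 24 hours; immediately |
| 11.1.1 | Yes, if within 4 weeks of last dose | Immediately |

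The reporting sentence stands alone against the other three. Nothing in the protocol says which text prevails.

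**Step 2. Is the exception workable as written?** No. Neither document defines disease progression for cystic fibrosis, and neither gives a separate route or deadline for deaths placed in that category.

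**Step 3. Which deaths does it reach?** Section 5.2 says severe pulmonary dysfunction is the usual cause of death in CF. The excepted category therefore overlaps both the most common cause of death in this population and the organ measured by the primary efficacy endpoint.

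**Step 4. What else brings such a death to attention?**

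- Section 11.1.3.1 requires the report independently.
- All adverse events in randomized patients go into the e-CRF (11.1.1), with a fatal outcome category (11.1.1.4).
- The DSMB receives adverse event reports with emphasis on serious events and exacerbations. It holds two unblinded active-versus-placebo safety reviews, otherwise meets every 6 months or as needed, and can obtain the randomization code if justified (7.2.2).

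**Step 5. Range of consequence.** At one end there is no delay, because the site follows 11.1.3.1. At the other, if one assumes that the expedited route is not used and nothing else prompts contact, a death could wait for the next scheduled DSMB review, nominally up to 6 months. The e-CRF and ad hoc meetings make that extreme unlikely. The documents give no expected number of deaths, so the number affected cannot be estimated.

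**The case against.** The best case for leaving the text alone has four parts.

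1. **The sentence already covers these deaths.** Its subject is any SAE, the phrase after the word including is only an illustration, and the definition makes a progression death an SAE. This reading is possible, but it leaves the words about disease progression with nothing to do. The text is at best ambiguous.
2. **Section 11.1.3.1 closes the gap.** It does require the report, which limits the practical risk. It also contradicts 11.1.3 directly, with no order of precedence, so it does not remove the need to reconcile them.
3. **The investigator must consult the medical monitor when classification is in doubt (11.1.3).** That helps in doubtful cases, but an investigator who is confident of progression has no doubt to raise.
4. **The stopping guideline carries no 24-hour clock and is only a guide.** This stands, and it limits what can be claimed.

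A reader might infer three stronger things that the documents do not support. One is that a progression death could go unreported altogether; no text permits that, and several routes in Step 4 would capture it. Another is that the stopping guideline could not be applied; it depends on a death being known and assessed, and a late report delays that without preventing it. The third is that a drug-induced respiratory decline could not be told from progression; Section 5.2 gives the usual cause of death and says nothing about distinguishing causes.

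Section 11.1.3 also lets the investigator judge that exacerbation events unrelated to study drug may not need expedited reporting. That adds to the unclear picture, but it does not mention death and is not the basis of this point.

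**Conclusion.** The inconsistency is real. The reporting sentence in 11.1.3 conflicts with the definition in its own section and with the reporting rules in 11.1.1 and 11.1.3.1. The consequence is a possible delay in an expedited report of a death, probably a respiratory one, that the DSMB chair should see in time to consider attribution and unblinding. A single death that may be attributable to the drug is enough to engage the guideline in 7.2.3, so the timing of even one report matters.

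The conclusion assumes that a site would read the phrase as an exclusion and act on 11.1.3 in preference to 11.1.3.1. How quickly a report then reaches the DSMB chair depends on the DSMB charter, which is not among the documents. Sample size, type 1 error and the efficacy analyses are untouched.

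**What to change.** Reconcile the definition and reporting sentence of 11.1.3 with 11.1.3.1 by deleting the last four words of "including death from any cause other than disease progression" from the reporting sentence. One 24-hour rule then covers every death during participation. The investigator's attribution, including any view that the death was due to progression, is recorded in the report and does not decide whether or when the report is made. The cost is a four-word deletion and at most a few extra expedited reports.

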11.1.3.1 Serious Adverse Event Reporting

It is imperative that the safety desk be informed within 24 hours of an SAE so that reporting to the health authority can be met within the required time frame.

Because of the need to report to health authorities all serious adverse reactions in a timely manner, it is vitally important that an Investigator report immediately any adverse experiences which would be considered serious, even if the Investigator does not consider the adverse experience to be clinically significant or drug related. Should the Investigator become aware of an SAE (regardless of relationship to study drug) that occurs within 4 weeks after the last dose of the study drug, the SAE must be reported in accordance with the procedures specified in this protocol.

All SAEs that are not resolved by the end of the study, or that were not resolved upon discontinuation of the patient's participation in the study, are to be followed until the AE resolves, the AE stabilizes, the AE returns to baseline values (if a baseline value is available), or it is shown that the AE is not attributable to the study drug or study conduct. If a patient or a female partner of a patient becomes pregnant during the study, the patient will be removed from the study without receiving further study medication. Follow-up regarding the outcome of the pregnancy and any postnatal sequelae in the infant is required. Pregnancies are considered immediately reportable AEs (within 1 working day) and are to be documented in the e-CRF.

11.1.3.2 Suspected Unexpected Serious Adverse Reactions (SUSAR)

SUSARs are SAEs that are possibly related or related to the study drug and are unexpected (i.e., not listed in the investigator brochure). SUSARs will be collected and reported expeditiously to competent authorities and independent ethics committees (IECs)/institutional review boards (IRBs) according to regulations. Medical and scientific judgment is to be exercised in deciding whether expedited reporting is appropriate in other situations, such as for important medical events that are not immediately life threatening or do not result in death or hospitalization, but jeopardize the patient or the patient population.

11.2 Clinical Laboratory Assessments

Blood and urine samples will be collected according to the Schedule of Events (page 10) and analyzed at the central laboratory [REDACTED]. Specific instructions for the collection, processing, and shipment of samples are presented in the Study Reference Manual. Laboratory test results that are abnormal and considered clinically significant must be reported as AEs (as per Section 11.1.1). Screening laboratory results must be available and reviewed by the Investigator before randomization. The safety laboratory test panels are shown in Table 1 below:

Table 1: Laboratory Tests Panels

Serum Chemistry	Hematology	Urinalysis*
Albumin	Hematocrit	Nitrite
Creatinine	Hemoglobin	Urobilinogen
Total protein	Red blood cells	Protein
Potassium	Mean corpuscular hemoglobin	pH
Sodium	Mean corpuscular hemoglobin	Blood
Calcium	Mean corpuscular volume	Leucocyte esterase
Bicarbonate	Reticulocytes	Specific gravity
Phosphate	Platelet count	Ketones
Alkaline phosphatase	Leucocytes	Bilirubin
ALT	Differential (absolute and %)	Glucose
AST	Eosinophils	Appearance
GGT	Basophils	
Total bilirubin	Neutrophils	
Blood urea nitrogen	Lymphocytes	
Glucose	Monocytes	
Total cholesterol		
LDL cholesterol		
HDL cholesterol		
Triglycerides		

* If urine is positive for leukocyte esterase, nitrite, urobilinogen, protein, or blood, microscopic examination of urine will be performed for leukocytes, erythrocytes, crystals, bacteria, and casts.

For the purpose of this study conduct, the laboratory tests performed in the central laboratory are the primary tests. Local laboratories may be used at the discretion of the local Investigator for management of emergent urgent medical conditions. If a local laboratory test result is found to be abnormal and clinically significant, it should be verified by the central laboratory as soon as possible after the Investigator is made aware of the abnormal test result. The Investigator may base the assessment of an AE on the local laboratory value if it is not possible to send a sample and obtain a timely report back from the central laboratory.

In addition, according to the Schedule of Events, the following tests are also performed:

- CF genotype (Screening Period only): If not already on file for the patient, CF genotyping will be performed locally.
- Pregnancy (β -human chorionic gonadotropin) tests for females of childbearing potential: Serum or urine samples will be obtained as specified in the Schedule of Events, page 10 and analyzed at the central laboratory (serum) or locally (urine). The urine pregnancy test on Day 1 must be negative before the first dose of study drug. A positive result during the study will result in immediate interruption of study drug.
- Follicle-stimulating hormone (FSH; Screening Period only): Blood sample for FSH will be measured for any suspected postmenopausal female with at least 12 months of continuous spontaneous amenorrhea. Serum FSH levels must be ≥ 40 mIU/mL to be considered postmenopausal.
- Plasma retinol and retinol binding protein: while this is to support an exploratory correlation with ophthalmological assessments, measurements may be used to support decisions made in relation with ophthalmological TEAe. Abnormal values may result in ad-hoc follow-up determinations, when associated with ophthalmological TEAe. Post-screening results will not be communicated to blinded staff, in order to maintain the study blind, unless required for emergency reasons.

Finally, clinical laboratory evaluations may be performed at other times if judged to be clinically appropriate by the Investigator.

